5. Please list all Research Sites in addition to Louis Stokes Cleveland DVA Medical Center (LSCDVAMC); The Cleveland VA is our site. [name] at Duke University and the Durham VA will also be funded by Merck and run 30 subjects there. He will send us coded blood samples to analyze with our samples. His samples will come from the Duke University site not their VA.

International studies when the PI is the Lead Investigator list the countries:

a. When study procedures including analysis of identifiable samples or data involving LSCDVAMC enrolled subjects will be conducted at any site other than the LSCDVAMC please provide the following:

Name and contact information for the site:

Describe the plan for communicating protocol amendments, reports of serious adverse events, reports of unanticipated problems involving risks to subjects or others, interim reports, and DSMB reports to external sites.

* When the LSCDVAMC is considered the coordinating center and the PI the lead investigator on cooperative research or a multi-center trial contact AO/Research [contact].

6. Sponsor or other Support (list industry sponsor, government support, etc.):

Merck

Section 3 – Research Design and Procedures

7. Definitions- Provide a list of all abbreviations and specialized terms to be used in this document and their definitions:

Abbreviations / Specialized Terms (Use the Enter key in this column to insert additional abbreviations and their definitions)	Definition
LSCDVAMC	Louis Stokes Cleveland DVA Medical Center
VZV	varicella zoster virus
HZ	Herpes Zoster
CMI	cell mediated immunity
ZOSTAVAX	Trade name for the shingles vaccine
XRT	X-Ray Therapy
chemo	chemotherapy

8. Provide a BRIEF SUMMARY of the background for this research. DO NOT CUT and PASTE paragraphs that do NOT summarize the background.

- *Include a critical evaluation of existing knowledge, and specifically identify the information gaps that your protocol is intended to fill.*
- *Refer to appropriate citations in the scientific literature and include your references at the end of this section.*
- *Include the rationale for conducting the research at the VA.*

The incidence of Herpes Zoster (HZ), caused by reactivation of VZV from sensory nerve ganglia, rises markedly after the sixth decade of life or as a result of impaired cell-mediated immunity (CMI). There are an estimated one million cases of herpes zoster in the United States annually [1]. ZOSTAVAX was approved by the FDA in 2006 [2] for immunocompetent adults over the age of 60 after the Shingles Prevention Study demonstrated efficacy at 51% [3] and in 2011 for adults over the age of 50 after a randomized controlled trial in 50-59 year olds demonstrated efficacy at 69.8% [4]. The Center for Disease Control and Prevention's (CDC) Advisory Committee on Immunization Practices (ACIP) recommends the vaccine for immunocompetent adults over the age of 60.

The risk of HZ increases with age and among those with impaired immunity. VZV infections continue to represent a significant source of morbidity among patients with cancer. In population based studies, cancer has been identified as the most common risk factor for the development of HZ infection [5, 6]. While those with hematologic malignancies, particularly those receiving hematopoietic stem cell transplant bear the greatest burden of HZ, individuals with solid organ tumors remain at significantly increased risk of zoster compared to general population. In another large study of 14,670 cancer patients compared with incidence rates of HZ reported in a general US population, the age- and sex-standardized rates of HZ was 1.9 times higher in those with solid tumors [7]. Another study found a two-fold increased risk of HZ from baseline in this population and further increase in risk to three-fold among those receiving chemotherapy with a median age at infection of 59 years [5]. In a study that investigated VZV infections in solid tumor patients undergoing chemotherapy, the incidence was 2.2% for patients receiving adjuvant chemotherapy and 6.2% in those undergoing palliative chemotherapy [8]. In one population based study the median time from the completion of chemotherapy to the onset of infection was less than one month [9]. Not only does HZ occur more frequently in individuals with impaired host defense mechanisms, they are also more likely to have disseminated disease and complications than immunocompetent hosts [7, 10].

2. We hypothesize that the fold increase in Varicella Zoster Virus (VZV)-specific immunity in subjects with solid organ tumors that were given ZOSTAVAX at least 14 days prior to initiation of chemotherapy will be higher than the control group that is not vaccinated.
3. We hypothesize that immediately before the second cycle of chemotherapy VZV-specific immunity will be higher in those subjects that received ZOSTAVAX prior to chemotherapy than those that were not vaccinated.
4. We hypothesize that at 3-18 months post-chemotherapy VZV-specific immunity will be higher in those subjects that received ZOSTAVAX prior to chemotherapy than those that were not vaccinated.
5. We hypothesize that ZOSTAVAX is safe if given to subjects with solid organs tumors at least 14 days prior to initiation of chemotherapy or surgery followed by chemotherapy.

10. Describe the means of analyzing the data and evaluating the results.

- *State the anticipated methods to be used for analysis and interpretation of the data.*
- *The methods must compliment the design of the study and the nature of the data which is being collected.*

Fold change will be the primary immune analysis and will be calculated for each individual subject based on their day 0 spot forming units on ELISPOT assay. Fold change will be calculated at each time point (chemo initiation, during chemo, 3 months post). This will take place in both the vaccinated and control (non-vaccinated) groups. The control group will have responses measured as well and is the essential comparison group to see how the responses change in relation to the vaccinated group through the pre, during, and post chemotherapy time points. As this model reflects a 2 group by 3 time point design, our initial overall assessment of the data will use a 2X3 Repeated Measures ANOVA (RMANOVA) to identify mean differences between groups, within time mean differences, and the interaction between groups and time to identify if the trends in the means over time is different for groups (vaccine vs. no vaccine). For the next step to gain a better understanding of how well the vaccine works at each time point (Hypothesis 2-4), we will use independent samples t-tests to analyze group mean differences at each time point separately to gain a better understanding of how the groups may be different at chemotherapy initiation, during chemotherapy, and at 3-24 months post-chemotherapy. Additionally, if we identify a significant interaction between group and time points, we will run follow-up RMANOVAs for each group separately to identify not only mean difference over time, but also linear (e.g. a steady increase or decrease in mean scores over time) and quadratic (e.g. a high mean scores at chemotherapy initiation, followed by a decline in mean score during chemotherapy, followed by a steady increase in mean score at 3-24 months post-chemotherapy) trends in the

means over time for each group. Violations of the assumptions for each analysis will be tested and the data will be transformed or the nonparametric equivalence analysis will be used when appropriate.

We will also perform multiparameter flow cytometry analysis on the cells to measure in greater detail what subtypes of T cells are responding. If there are sufficient PBMC available we will perform transcriptomic analysis of vaccine-induced gene changes over the time course of the study. Antibody titers may also be assessed as they are of historical interest in zoster and there is significant data on changes in antibody titers as at least a measure of immunologic response.

A portion of the sample may be sent to our collaborators at University of Pennsylvania (Drs. [name] and [name]), or Vaccine and Gene Therapy Institute in Port-St-Lucie, FL ([name], coming to CWRU this Fall to join our faculty), and Merck's immune assay unit (Swiftwater, PA) as each of these collaborators perform assays that we do not perform at the VA in the [name] laboratory. Any samples that are sent will be coded with no personal identifiers. The cells going to Penn will have advanced T cell marker analysis and cloning, to [name] they will have transcriptomic analysis, and to Merck they will have anti-VZV glycoprotein ELISA performed. Samples will be destroyed in Cleveland and at the other sites after the assays are performed.

11. Provide a BRIEF DESCRIPTION of how the estimated number of study subjects needed for this research was determined

- *If this is a quantitative study provide the method of determining sample size estimates.*
- *If multiple studies are planned provide a power analysis or justification for each one.*

This is a pilot study so precise sample size calculations are not possible since the data do not exist yet to determine this. Obtaining this pilot data is one of the key purposes of this study. For the primary analysis: If we anticipate some loss of subjects for various reasons beyond our control so that we hope to end up with about 76 subjects for full analysis after initially enrolling 90 subjects. This is based a projection of receiving up to 30 coded samples from our collaborator [name] at Duke University who is running a similar study at that site and initially enrolling 60 from Cleveland. Using G*Power to perform a sample size calculation with 76 subjects (38 vaccinated and 38 un-vaccinated assuming some loss due to lack of all 4 timepoints) and an analysis comparing these two groups at the 3 time points to test Hypothesis 1 using a 2 x 3 Repeated Measures ANOVA with power 0.8 and α error 0.05 we can detect an effect size of 0.27. For independent t-tests analyzing mean differences at each individual time point we would be able to detect an effect size of 0.58. For both of these types of analyses our power is near a medium effect size. The data from this pilot study will inform the sample size for a larger future study.

12. The research involves the following procedures conducted by and for what purpose:

[figure not shown]
PROCEDURE	PERFORMED BY:		PROCEDURE IS:	
	Research Staff	LSCDVAMC Clinical or Support Staff	Standard of Care*	For Research Purposes Only**

PROCEDURE	PERFORMED BY:		PROCEDURE IS:	
	Research Staff	LSCDVAMC Clinical or Support Staff	Standard of Care*	For Research Purposes Only**
Audiotaping / Videotaping Attach VA Form 10-3203 REQUIRED ONLY FOR IN-PATIENT AND OUT-PATIENT SUBJECTS				
Biopsy				
Blood collection				
Chart review – prospective (FOR pre-SCREENING)				
Chart review – retrospective				
Review of existing data (ex: registry, Database , etc.)				
X-ray or Ionizing radiation exposure				
Clinical Tests				
Device implantation				
Drug administration				
EEG, EKG , ECG...etc				
Gene therapy, Genetic analysis				
Pregnancy/Breastfeeding Screening				
Interview, Questionnaire, Diary, Survey (please attach)				
Stool collection, Urine collection, or any Non-surgical Specimen collection				
Surgical procedure or Specimen removal during surgery				
Tissue banking (complete Section 12)				
Use of pre-existing tissues/specimens				
Other (list):				

- **Standard of care procedures are procedures performed in the course of normal medical care.*
- ***Research Procedures are performed for the purposes of this research alone.*

13. Please describe the research design and all study related procedures.

- Describe ALL PROCEDURES ASSOCIATED WITH THIS RESEARCH. This includes standard of care and research procedures.
- For complex studies please include diagrams and tables. Be sure to describe when each procedure will be performed. Be sure to provide information for each cohort, including normal controls.

Study participants based on the inclusion and exclusion criteria listed below will be recruited from the Oncology clinics and medical services of the Cleveland VA. The study oncologist will review the study with them. Subjects that consent will be randomized to one of the two arms, vaccine or no vaccine. Individuals will undergo blood draws for immunologic assays according to time points depicted in the figure below. Each blood draw (25 ml each) has been timed to follow routine clinical monitoring as ordered by the oncologist for maximum feasibility.

- The first blood draw will be at the time of consent into the study. We anticipate this time to be the first visit with the oncologist. They will receive ZOSTAVAX on that day if they are in that arm of the study.
- The second blood draw will be on the day of chemotherapy initiation, no earlier than 14 days post-vaccination. This will be longer than 14 days for example when there is surgery between the vaccination and the start of chemotherapy.
- The third blood draw will be at the start of the second chemotherapy cycle.
- The fourth blood draw will be 3-24 months post chemotherapy cessation. The timing of the final blood draw is based on cessation of chemotherapy and not any concurrent radiation therapy that would be also completed by the 3-6 month post-chemotherapy sampling.

The subjects chemotherapy is decided by the Oncologist and/or Tumor Board in consultation. The duration of chemo similarly is also decided clinically. If the patient needs surgery or XRT

as part of the therapy, it is decided on entirely by the clinicians. The study is working around all of these clinical decisions.

Subjects will be called between visit 2 and 3 and then between visits 3 and 4. They will be asked if they had a side effects or event that may have been serious since the last study visit or telephone contact. They will also be asked if they were exposed to anyone who has chickenpox or shingles, and if they had any symptoms of shingles.

For 4 weeks after they receive their shot, they will be asked to record information about potential vaccine side effects on the vaccination Report Card.

14. Will the research involve the following?

N/A Chart/Data Review

Placebo Group No Yes (describe):

Other Control Group No Yes (describe): The control group is persons that do not get the vaccine.

Randomization No Yes (describe): We will obtain clinical information to determine eligibility this includes meds and PMH and then follow the subject's clinical course to know when to do the subsequent sampling. We will use a cloud based randomized tool to generate the list before the start for the whole study for what the order of vaccine or no vaccine will be. We will then have paperwork packets in the order of enrollment premade. We will open each packet at the consenting time and find vaccine or not and enroll and begin the study.

Deception No Yes (describe):

15. Does the research involve the use and/or disclosure of Individually Identifiable Health Information in any form or medium?

No Yes If yes, complete the required HIPAA Waiver/Authorization forms.

16. Does the study include the administration of a study agent that does not require FDA approval and does not require an IND (e.g. vitamins, food supplements, isotope tracers, alternative medicines, etc.)?

No Yes -provide a detailed description of the procedures used to assure patient safety:

17. Will radioactive material be administered or will subjects be exposed to ionizing radiation?

• Ex. Radiographic equipment, fluoroscopic equipment, and CT scanners, etc.

No Yes

18. In your judgment, could the objectives of the research be met in a way that presents less risk to subjects?

No Yes please explain:

Section 4 – Subject Selection, Recruitment, and Vulnerable Populations

19. Anticipated duration of entire study reported in years: 5

20. Estimated number of subjects to be studied at the LSCDVAMC or charts/records to be reviewed.

- Provide answers for each cohort including normal controls; (patients, family members, treating physicians,):

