No Yes- explicitly describe your process for identifying and/or recruiting these patients: (address all cohorts): See the answer for question 27. We will focus on subjects with recent cancer diagnosis that will be seen in the clinics of oncology or by their inpatient team. We can assist the oncologists in prescreening for suitability to the study. Also the coordinator and Co-I may discuss with the medical teams about our study that we are searching for subjects with oncology diagnosis that will receive chemo soon and the primary providers then may refer subjects to us to screen.

29. In addition to the consent form will any other materials be given to the subject?

N/A Chart/data review

No Yes- check all that apply and submit for IRB review:

Letter

Information Sheets

Questionnaire, Survey, Diary

Other (flyer, brochure, describe): If they enroll they will fill out the vaccine report card.

30. Please list by bullet point inclusion/exclusion criteria for the study.

- *Entry criteria should be as detailed as necessary to define the subject population(s) under study and reduce confounding design. Include precise criteria for age, gender, and other relevant factors.*
- *List specific exclusion criteria which could interfere with the study design or place a subject at risk during the study.*
- *Provide answers for each cohort, including normal controls.*

Inclusion criteria:

- Solid organ tumor patients that have at least 14 days between entry into the study with ZOSTAVAX vaccination and initial therapy for their malignancy that will include chemotherapy alone or surgery with subsequent chemotherapy plus or minus radiation therapy.
- A plan for chemotherapy that at the onset at least has an anticipated stop date within 3-6 months of our sample collection phase of the study.
- Age 50 or older

Exclusion criteria:

- Prior history of HZ or shingles vaccine
- Systemic chemotherapy <3 months prior to enrollment
- Any history of hematologic malignancy, HIV/AIDS, hematopoietic stem cell transplant, or other cellular immunodeficiency state
- Those receiving immunomodulating drugs at the time of vaccination such as prednisone, methotrexate, azathioprine, mercaptopurine, or other biologics including TNF- α inhibitors
- Widespread metastatic tumor with bone marrow involvement
- Indefinite duration palliative chemotherapy subjects
 - Inability to communicate with the study staff or being unable to consent for themselves.

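### Draw 4 is timed only from the end of chemotherapy, so samples taken under later radiation or drug treatment enter one post-chemotherapy level without being identified

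*Protocol*

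**What the plan says.** Protocol Section 3, item 13 sets the window: "The fourth blood draw will be 3-24 months post chemotherapy cessation". It then says the timing is "based on cessation of chemotherapy and not any concurrent radiation therapy that would be also completed by the 3-6 month post-chemotherapy sampling". Whether surgery or radiation is needed "as part of the therapy, it is decided on entirely by the clinicians", and "The study is working around all of these clinical decisions".

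Item 30 admits patients planned for chemotherapy alone or "surgery with subsequent chemotherapy plus or minus radiation therapy"; it does not require the radiation to be concurrent. It also excludes "Those receiving immunomodulating drugs at the time of vaccination such as prednisone, methotrexate" and similar agents including biologics, but only at that one time.

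Item 14 says staff will "follow the subject's clinical course to know when to do the subsequent sampling". The telephone calls in item 13 ask about side effects or serious events, exposure to chickenpox or shingles, and shingles symptoms. They do not ask about new treatment.

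Protocol item 10 and SAP 2.7 use draw 4 as the third level of a 2 x 3 repeated measures ANOVA and in its own t-test. Neither mentions treatment received between the end of chemotherapy and the draw.

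**The concern.** Protocol item 8 gives the durability of cell-mediated immunity after chemotherapy as part of the study's topic. Hypotheses 1 and 4 and the quadratic-trend example in item 10 and SAP 2.7 rest on draw 4 as the reading once chemotherapy is over. A sample taken during second-line treatment, or while radiation is running, reflects immunity under renewed treatment. The rule accepts both kinds of sample, and the analysis has no planned variable to tell them apart.

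A weak result at draw 4 could then mean that the vaccine response faded, or that some patients were being treated again. The trial is a pilot meant to inform the size of a larger study, so that ambiguity would carry forward.

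**Working it through.** **Does the text close the gap?** Setting the provisions side by side:

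- *Radiation.* The premise covers concurrent radiation only. Eligibility permits radiation without fixing its order, and clinicians decide it. Radiation after chemotherapy is therefore permitted but not addressed.
- *Window.* The premise refers to sampling at 3-6 months, but the same bullet allows 24. Elsewhere the time point is 3-6 months (Hypothesis 1), 3-18 months (Hypothesis 4), both 3 months and 3-24 months (item 10), and 3 months (SAP 2.7). A longer window leaves more time for new treatment.
- *Drugs.* The immunomodulator exclusion applies at vaccination, not at draw 4.
- *Data.* The clinical course is followed in order to time samples. No use in the analysis is stated.
- *Removal.* Item 65 ticks worsened condition and investigator's judgment as possible grounds. It does not name new therapy.

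The gap remains.

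**The plan's own figure.** Inputs from Protocol item 11 and SAP 2.7: 38 per arm, alpha 0.05, power 0.80, detectable effect 0.58 for a t-test at one time point. Using the noncentral t with 2 x 38 - 2 = 74 degrees of freedom and noncentrality d x sqrt(38/2) = 4.359d:

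- one-sided: detectable d = 0.576; power at 0.58 is 0.805
- two-sided: detectable d = 0.651; power at 0.58 is 0.704

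The stated 0.58 therefore matches a one-sided test. The documents do not state sidedness, so both are shown below.

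**Illustrative dilution.** Assume a share q of draw 4 samples in each arm is affected, and the vaccine effect in those samples is reduced by a fraction a. Holding the standard deviation fixed, the average effect is d' = 0.58 x (1 - q x a). Both q and a are assumptions.

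| q | a | 1 - qa | d' | Power, one-sided | Power, two-sided |
|---|---|---|---|---|---|
| 0 | - | 1.00 | 0.580 | 0.805 | 0.704 |
| 10% | 50% | 0.95 | 0.551 | 0.769 | 0.659 |
| 10% | 100% | 0.90 | 0.522 | 0.729 | 0.612 |
| 20% | 50% | 0.90 | 0.522 | 0.729 | 0.612 |
| 20% | 100% | 0.80 | 0.464 | 0.640 | 0.514 |

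**Leaving affected samples out instead**, with d = 0.58 in the rest:

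- 10% out: 38 x 0.9, about 34 per arm; power 0.765 one-sided, 0.654 two-sided
- 20% out: 38 x 0.8, about 30 per arm; power 0.717 one-sided, 0.598 two-sided

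In the mildest case exclusion gains no power (0.765 against 0.769). Its value is in interpretation.

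**Does dilution follow?** Not necessarily. Suppose later treatment multiplies responses by a factor c in both arms. On the raw fold-change scale the difference in affected samples becomes c x (vaccine mean - control mean), which shrinks if c is below 1. On a log scale c cancels. The plan transforms the data only if assumptions are violated, so either case could arise.

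**The case against.** The strongest reply is that allocation is randomized. Later treatment can occur in both arms, and a comparison that keeps every sample is valid whatever treatment followed. Hypothesis 4 asks only whether immunity is higher in the vaccinated arm after chemotherapy; it does not require freedom from later therapy. This stands. A reader might infer that the plan biases the vaccine comparison; the documents do not support that.

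A reader might also infer that affected samples are common and certainly dilute the effect. The documents give no rate and no evidence that later treatment reduces VZV responses or the arm difference, so dilution is possible but not shown.

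There are partial safeguards. Item 30 requires an anticipated chemotherapy stop date and excludes indefinite palliative chemotherapy and widespread metastatic tumor with marrow involvement. Item 65 allows removal for a worsened condition, so some progressing patients would never reach draw 4. If chemotherapy restarts, it is undefined whether the clock restarts too, so one cannot say that the rule always accepts such a sample. These points narrow the problem. They leave radiation after chemotherapy, steroids and biologics uncovered, and discretionary removal can itself change who is sampled.

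Finally, a pilot is not judged mainly on power. That is fair, but a pilot's estimates need a clear meaning if they are to size the next study. The time-point figure mentioned in item 13 could not be read; if it restricts draw 4 further, the point narrows.

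**Conclusion.** The concern holds in limited form. The draw 4 rule pools samples taken after treatment with samples taken under renewed treatment, and no planned data item separates them. This blurs what draw 4 says about durability after chemotherapy and about the time trend. It does not invalidate the randomized comparison when all samples are kept.

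The size is unknown. Under the assumed 10-20% affected with 50-100% loss of effect, one-sided power goes from 0.80 to about 0.77-0.64 (two-sided, from 0.70 to about 0.66-0.51). The lower ends are worst cases that assume no vaccine effect at all in affected samples, and the calculation ignores any added variance. The change is worth making because it costs little.

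**What to change.** 1. **Protocol items 9, 10 and 13, and SAP 2.7:** reconcile the draw 4 windows, and state whether restarted chemotherapy resets the sampling clock.
2. **Protocol item 13:** add wording such as: *Draw 4 is taken at the first routine visit in the window. If radiation is still under way when the window opens, it is taken after that radiation ends, where the window allows. If new radiation or systemic anticancer treatment is planned, it is taken before that treatment starts, where feasible. Clinical care is not altered to fit the draw.*
3. **Data collection:** record from the chart, with dates, all radiation, systemic anticancer drugs, steroids and biologics between chemotherapy cessation and draw 4. Research chart review is already ticked in item 12.
4. **SAP 2.7:** keep all samples in the main analysis of Hypotheses 1 and 4. Add a sensitivity analysis without draw 4 samples taken under such treatment. Report the number left out by arm, and state that the analysis conditions on a post-randomization event and may select different patients in the two arms.

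Cost: a few sentences, one chart entry per subject, one further analysis and some scheduling effort. Earlier draws also shorten the durability follow-up for some subjects. Only a research blood draw moves.

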****If yes complete the following:**

a. The LSCDVAMC investigator will send:

- Hardcopy information or specimens
 Electronic information

b. What are the procedures for transporting and/or transmitting identifiable information securely?

c. What will be the final disposition of the identifiable data transferred offsite?

- Record Control Schedule 10-1 indicates that all research records must be retained indefinitely

Records will be maintained indefinitely or until the RCS-10 is updated.

62. Record Control Schedule 10-1 indicates all research records must be retained indefinitely. Please indicate where this information will be stored and the safe guards to protect it:

a. Electronic Safeguards:

- No electronic data will be stored
 VA encrypted laptop
 Encrypted VA device/media- describe:

- VA network drive;
 - M: drive; whose?
 - S: drive
 - Folder access password protected
 - Other drive location (for example P: drive):
 - Folder access password protected

b. Hardcopy safeguards. Two locking barriers must be in place.

- No hardcopy data will be stored
- Locked Office and Locked File Cabinet
- Coded by Study Staff
- De-identified by Privacy Officer or Statistician
- Other- Describe:

Facility name, address, and room number where hardcopy or electronic data will be stored:

For long term storage the paper will go to Wade Park VA, K203, [name] in a locked cabinet in [name] laboratory.

Section 8 – Data and Safety Monitoring – Greater than Minimal Risk Study

- For all research that is greater than minimal risk a Data and Safety Monitoring Plan must be developed.
- This is a plan to assure the research includes a system of appropriate oversight and monitoring of the conduct of the study to ensure the safety of subjects and the validity and integrity of the data.

*CHECK BOX IF THIS IS A MINIMAL RISK STUDY SKIP TO #65

63. Safety monitoring for this greater than minimal risk project will include:

- Data Safety Monitoring Board:
- Data Monitoring Committee
- Other

- *Attach the plan or provide details including whether committee is independent from the study sponsor, how often it meets, whether written reports are available, etc*

The PI, primary Co-I's, and Coordinators of the study (Cleveland and Duke) will correspond at least monthly and review the study and vaccine report cards for any sign of increased toxicity in this population.

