Safety and tolerability will be assessed by statistical and clinical review of all safety data collected throughout the study. All subjects who are vaccinated and provide any safety follow-up will be included in safety analyses and summaries. To provide an overall assessment, the incidence rate for the vaccination group and no-vaccination group, the risk difference between the two groups and the associated 95% CI will be provided for broader safety measures such as the proportions of the subjects with any: adverse experiences; injection-site adverse experiences; systemic adverse experiences; serious adverse experiences; or vaccine-related serious adverse experiences after vaccination.

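### As item 13 is written, three stretches of follow-up have no call or visit asking about side effects or serious events, and capture before chemotherapy may differ between arms

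*Protocol*

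**What the plan says.** Protocol item 13 sets four blood draws. The first is at consent, when the vaccine arm is also vaccinated. The second is on the day chemotherapy starts, at least 14 days after vaccination. The third is at the start of cycle 2, and the fourth is 3 to 24 months after chemotherapy ends. On the second draw it adds: "This will be longer than 14 days for example when there is surgery between the vaccination and the start of chemotherapy". No maximum is given.

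Safety contacts appear later in the same item: "Subjects will be called between visit 2 and 3 and then between visits 3 and 4". The question on side effects and possibly serious events covers the time "since the last study visit or telephone contact". A separate sentence adds questions on exposure to chickenpox or shingles and on shingles symptoms, with no look-back stated.

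There is also a Report Card: "For 4 weeks after they receive their shot, they will be asked to record information about potential vaccine side effects". Item 13 ties it to the injection, whereas item 29 says "If they enroll they will fill out the vaccine report card", which could include controls. Under item 63 the study teams correspond at least monthly and "review the study and vaccine report cards for any sign of increased toxicity in this population".

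Hypothesis 5 (item 9) is that the vaccine is safe when given at least 14 days before chemotherapy, or before surgery followed by chemotherapy. SAP section 2.7 states: "Safety and tolerability will be assessed by statistical and clinical review of all safety data collected throughout the study". It then plans incidences by group and risk differences with 95% CIs for adverse experiences of several kinds, including any, systemic and serious.

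**The concern.** The only dose is given at visit 1, yet the first call comes after visit 2, and its side-effect question reaches back only to visit 2. No text provides for asking that question at a visit. Taken literally, the interval between vaccination and chemotherapy has no call, and each call is followed by a stretch to the next visit that nobody asks about.

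Two things are at stake. First, events may be under-counted in both arms, above all between call 2 and the final draw, so a reassuring incidence would partly reflect not having asked. Second, the planned comparison assumes that both arms are observed alike. If only vaccinated subjects keep a card before chemotherapy, they will report more events than controls even when the true risks are equal.

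**Working it through.** The plan gives no figure for event capture, so there is none to reproduce. The check lays the collection windows on the visit timeline and then sizes the effect on the SAP comparison.

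**1. Windows for side effects and serious events (item 13, read literally)**

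| Stretch | Call or visit asking | Report Card |
|---|---|---|
| Visit 1 to visit 2 | none | vaccinated to day 28; controls unclear |
| Visit 2 to call 1 | call 1 | any part before day 28 |
| Call 1 to visit 3 | none | any part before day 28 |
| Visit 3 to call 2 | call 2 | normally ended |
| Call 2 to visit 4 | none | ended |

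**2. Visit 1 to visit 2**

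Unasked days in vaccinated subjects = max(0, gap − 28). Unasked days in controls without a card = the whole gap. The 14-day minimum is the protocol's; the longer gaps are assumed.

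| Gap (days) | Vaccinated | Controls, no card |
|---|---|---|
| 14 | 0 | 14 |
| 28 | 0 | 28 |
| 42 | 14 | 42 |
| 56 | 28 | 56 |
| 84 | 56 | 84 |

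**3. After each call**

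Assumptions: a 21-day cycle, 90 to 180 days of chemotherapy, and each call placed a fraction f = 0.25 to 0.75 of the way through its interval. The documents give none of these.

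- Call 1 to visit 3 = (1 − f) × 21: from 0.25 × 21 = 5 days to 0.75 × 21 = 16 days.
- Call 2 to visit 4 = (1 − f) × (chemotherapy days + days to visit 4 − 21).
  - Visit 4 at 3 months (91 days): from 0.25 × (90 + 91 − 21) = 40 days to 0.75 × (180 + 91 − 21) = 188 days.
  - Visit 4 at 24 months (730 days): from 0.25 × (90 + 730 − 21) = 200 days to 0.75 × (180 + 730 − 21) = 667 days.

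**4. Effect on the risk difference in visit 1 to visit 2**

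There are 45 per arm (30 Cleveland plus 15 Duke, items 20 and 21). Let both arms have the same true risk p, with full capture in the vaccine arm and a captured share s in controls.

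False difference = p − sp. Standard error = √[p(1 − p)/45 + sp(1 − sp)/45]. The interval is ±1.96 standard errors.

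- p = 10%, s = 0: +10 points; SE = √(0.09/45) = 0.0447; 95% CI 1.2 to 18.8.
- p = 30%, s = 0: +30 points; SE = √(0.21/45) = 0.0683; 95% CI 16.6 to 43.4.
- p = 30%, s = 0.5: +15 points; SE = √(0.21/45 + 0.1275/45) = 0.0866; 95% CI −2.0 to 32.0.

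The risks and capture shares are illustrations. When s = 0 the control variance term is zero, so those intervals are somewhat too narrow.

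**5. Scale of reassurance available**

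Zero events in 45 vaccinated subjects gives an upper limit of 1 − 0.025^(1/45) = 7.9% (two-sided 95%). That limit holds only for time in which events were asked about.

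**The case against.** The strongest reply is the Report Card. A reader might infer from the call schedule that events in the vaccine phase are never asked about. The documents do not support that: the card collects potential vaccine side effects for 4 weeks. For vaccinated subjects it spans the whole of visit 1 to visit 2 whenever chemotherapy starts by day 28.

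A reader might also infer that shingles and exposure go unasked in all three stretches. That is not supported either. Those two questions carry no stated look-back, so either call might reach back to day 0. For them the gap is firm only from call 2 to visit 4.

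Next, the look-back names the previous visit as an anchor, which makes most sense if subjects are also questioned at visits. The time-point figure and the attached questionnaires were not available to settle this. If call 2 were instead meant to reach back to call 1, the middle stretch would close; the other two would not. This is a fair reading, but item 13 asks for every procedure and its timing, and it does not say that the visits include these questions.

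Finally, item 12 ticks retrospective chart review, and the oncology co-investigators treat the subjects (item 54), so some serious events would reach the study anyway. Neither route is described as adverse-event collection, and how much it would recover cannot be judged from the documents.

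**Conclusion.** The point holds as a gap in the written schedule. Side effects and serious events are not solicited by call or visit in three stretches. The largest is call 2 to visit 4: 40 to 667 days across the assumptions above, and over a year in some cases. In visit 1 to visit 2, the vaccine-arm gap is limited to day 29 onward when surgery or another delay pushes chemotherapy past day 28. Controls have no solicited collection there if the card goes only to vaccinated subjects, which items 13 and 29 leave unclear.

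The direction of error is mixed. After call 2, under-counting affects both arms and favours reassurance. Before chemotherapy, unequal capture would push the risk difference against the vaccine.

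A reader might conclude that Hypothesis 5 cannot be answered soundly. That goes too far: vaccinated subjects' reactions in the first 4 weeks are collected and reviewed. The answer is weakened for later events and for the between-arm comparison. The size rests on the assumed cycle length, chemotherapy duration, call timing, risks and capture shares; the existence of the gap rests only on item 13 as worded.

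**What to change.** In item 13, state that the existing call questions (side effects, serious events, exposure, shingles symptoms) are put to both arms at visits 2, 3 and 4 as well as at the two calls. Each asking should look back to the last one. At visit 2 they should be asked before that day's chemotherapy and reach back to day 0. This leaves no stretch unasked in either arm.

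In SAP section 2.7, report events separately for day 0 to chemotherapy start and for after chemotherapy start. Say whether controls complete the card. If they do not, base the between-arm comparison for the first period on the question asked of both arms, and keep card data as a description of the vaccine arm.

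The cost is a few minutes and about one extra page at visits that subjects already attend. The downsides are slightly more data entry, a higher reported event count, and long recall at visit 4, which will blur dates and lose mild events. If the visits were always meant to include these questions, the change is a sentence of clarification.
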